#### 7.1.5. Model Fitting

The following types of models may be fit for the efficacy endpoints: Mixed-effect model for repeated measures (MMRM), generalized estimating equations (GEE), or logistic regression.

For the MMRM models, a single covariance structure will be applied to all MMRM analyses for an efficacy endpoint. Different covariance structures may be applied to different efficacy endpoints. For the Word Recognition in Quiet (WR) and Words-in-Noise (WIN) analyses, the covariance structure for each endpoint will be identified by comparing model fit for the relative percent change from baseline in percentage of recognized words using two different covariance structures (unstructured [UN] and autoregressive (1) [AR(1)]), as described in Section 7.3.4. For the audiometry analyses, the covariance structure will be identified by comparing model fit for the mean overall Pure Tone Average (PTA) using the two different covariance structures, as described for WR and WIN. For the Tinnitus Functional Index (TFI) analyses, the TFI total score will be used to identify the covariance structure for all TFI endpoint analyses. Covariance structures will also be identified for the Hearing Handicap Inventory for Adults (HHIA) and the Hearing Screening Inventory (HSI) analyses, separately, using the total scores. The covariance structures identified for the IA may be different than the covariance structures for the CSR analyses, based on the evaluation for model fit. Further details for each of the planned models and analyses are provided in subsequent sections.

Models and descriptive summaries for the IA will only include data through Visit 5 (Day 90). Data through Visit 9 (Day 210) will be included in the models and summarized descriptively for the CSR.

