#### 7.3.4. Relative percent change from baseline in percentage of recognized words

- *Computation of the Endpoint*

The relative percent change from baseline to each post-baseline visit in percentage of recognized words will be computed as  $100 * [(w-b)/b]$  where “w” is the frequency of words recognized at the post-baseline visit and “b” is the frequency of words recognized at baseline.

- *Analysis of the Endpoint*

The relative percent change from baseline in percentage of recognized words will be summarized descriptively for treated and untreated ears using the approach described in Section 7.3.1 for subjects in the FAS.

Line graphs (with standard error bars) for the adjusted (least squares) means and observed means will be created using the approach described in Section 7.3.3 for subjects in the FAS.

In treated ears only for subjects in the FAS, treatment group comparisons for the relative percent change from baseline in percentage of recognized words will be analyzed using a mixed-effect, repeated measures model using fixed covariates for treatment group, WR score at baseline (<50% versus >=50%), etiology of hearing loss (SSNHL versus NIHL), visit, and interaction between visit and treatment group. Separate models will be fit specifying UN and AR(1) covariance structures (implemented with a repeated statement in SAS). The covariance structure providing the lowest corrected Akaike’s Information Criteria (AICc) and Bayesian Information Criteria (BIC) values from the model will be implemented for the relative percent change from baseline and all other WR endpoints. The treatment group differences analyzed will be between each FX-322 group (including the pooled FX-322 group) versus placebo, and comparisons between the individual FX-322 groups (excluding the pooled FX-322 group). Comparisons will be made by visit (e.g., estimated Least squares (LS) Mean differences by visit) and overall (e.g., Type III Sums of Squares).

- *Sensitivity Analyses of the Endpoint*

With the exception of the line graphs, the analyses will be repeated for subjects in the PPAS.

The possible presence of site-to-site heterogeneity will be evaluated using the approach described in Section 7.3.2 for subjects in the FAS.

If there are any dosing administrations errors such that a not qualified ear is treated, the descriptive summaries by treated and untreated ears will be repeated for subjects in the FAS including all treated and untreated ear data.

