#### 7.5.5. Mean overall PTA (AC over 0.5, 1, 2, and 4 kHz) and BCA (BC over 0.5, 1, 2 and 4 kHz)

- *Computation of the Endpoint*

At each visit and by ear (left, right), the mean overall PTA will be derived by averaging the AC audiometry dB hearing thresholds over 0.5, 1, 2, and 4 kHz frequencies. Left and right ears will be mapped to treated and untreated for analysis, as described in Section 3. Missing values will be imputed per Section 7.5. The BCA will be derived using the same approach. If hearing thresholds are missing for any of the 0.5, 1, 2, and 4 kHz frequencies (after imputation of records with classification of "NR"), PTA or BCA will be missing, respectively.

Mean overall PTA for each ear will be categorized into  $<26$ , 26-40, 41-55, 56-70, and  $>70$  for each visit and shifts from baseline to each post-baseline visit will be computed (e.g., 26-40 to 41-55).

- *Analysis of the Endpoint*

The mean overall PTA will be summarized descriptively for treated ears separately by visit and treatment group for subjects in the FAS. The summary will be repeated for BCA.

In treated ears only for subjects in the FAS, treatment group comparisons for mean overall PTA will be analyzed using a mixed-effect, repeated measures model using fixed covariates for treatment group, WR score at baseline ( $<50\%$  versus  $\geq 50\%$ ), etiology of hearing loss

(SSNHL versus NIHL), visit, and interaction between visit and treatment group. As described in Section 7.3.4, separate models will be fit specifying UN and AR(1) covariance structures (implemented with a repeated statement in SAS). The covariance structure providing the lowest corrected AICc and BIC values from the model will be implemented for the PTA and all other audiometry endpoints. The treatment group differences analyzed will be between each FX-322 group (including the pooled FX-322 group) versus placebo, and comparisons between the individual FX-322 groups (excluding the pooled FX-322 group). Comparisons will be made by visit (e.g., estimated LS Mean differences by visit) and overall (e.g., Type III Sums of Squares). The treatment group comparisons will also be performed for BCA.

The distribution in the shift in mean overall PTA categories for treated ears from baseline to each post-baseline visit will be summarized using frequencies and percentages by visit and treatment group for subjects in the FAS.

- *Sensitivity Analyses of the Endpoint*

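### The covariance rule for the MMRMs asks for the lowest AICc and BIC between UN and AR(1), gives no answer when the two disagree, and can let in a structure that understates the standard error of the overall contrast.

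*SAP*

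**What the plan says.** For WR, SAP 7.3.4 fits the relative-change model twice: "Separate models will be fit specifying UN and AR(1) covariance structures (implemented with a repeated statement in SAS". The structure with the lowest AICc "and Bayesian Information Criteria (BIC) values from the model will be implemented for the relative percent change from baseline and all other WR endpoints". SAP 7.4.4 does the same within WIN. SAP 7.5.5 uses the PTA: "The covariance structure providing the lowest corrected AICc and BIC values from the model will be implemented for the PTA and all other audiometry endpoints". SAP 7.7.1 and 7.8.1 use the TFI and HHIA total scores, and 7.9.1 carries the same sentence for HSI.

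SAP 7.1.5 confirms which variable drives each choice. For WR and WIN, "the covariance structure for each endpoint will be identified by comparing model fit for the relative percent change from baseline in percentage of recognized words". It then adds: "The covariance structures identified for the IA may be different than the covariance structures for the CSR analyses". Comparisons are planned by visit and overall.

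The SAP does not say what happens if AICc and BIC favour different structures. For the MMRMs it gives no other structure, no robust standard error, no degrees-of-freedom method and no fallback for non-convergence. The GEE models do have a convergence rule.

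SAP 7.1.4 treats all p-values as descriptive, and 7.2 names no primary endpoint.

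**The concern.** **The rule is incomplete.** AICc and BIC penalise UN's extra parameters very differently. When the fit improvement falls between the two penalties, the SAP gives no answer and someone must choose.

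**One candidate fits the design poorly.** AR(1) treats Days 15, 60, 90, 150 and 210 as equally spaced, although the gaps are 45, 30, 60 and 60 days. It assumes one variance and a correlation that decays towards zero. Every change score subtracts the same Screening value, and raw scores carry stable differences between subjects. Both produce correlation that does not decay. AR(1) then credits the average over visits with more information than it holds.

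**The choice is carried over.** The structure picked on relative percent change is imposed on word counts, percentages, absolute change and arcsine scores, whose correlation may differ.

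The comparisons between dosing schedules are read from these standard errors and intervals, so they should be right even in an exploratory trial.

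**Working it through.** The documents give no variance, correlation or power figure, so there is nothing of the plan's own to reproduce. Every error rate below depends on the assumption stated with it.

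**Inputs.** 96 subjects, 24 per group (SAP 2.4, 6.2). Five post-baseline WR visits (SAP 7.3), three at the Day 90 interim. Fixed effects as in SAP 7.3.4: 4 × 5 = 20 group-by-visit means plus 2 covariates, p = 22. UN has 15 covariance parameters and AR(1) has 2. I assume the usual REML conventions: AICc with n* = observations - p, BIC with n = 96 subjects.

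**1. Thresholds.** The AICc penalty is 2d·n*/(n* - d - 1), with n* = 480 - 22 = 458.
- UN: 30 × 458/442 = 31.09. AR(1): 4 × 458/455 = 4.03. Difference 27.1.
- BIC difference: (15 - 2) × ln 96 = 13 × 4.564 = 59.3.
- Three visits, by the same formulas: 8.3 and 18.3.

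A gain in -2 log-likelihood between 27.1 and 59.3 leaves the five-visit rule without an answer.

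**2. Expected gain under constant correlation ρ (compound symmetry).** The best-fitting AR(1) matches the adjacent correlation. The systematic gain per subject is therefore 4·ln(1 - ρ²) - ln[(1 - ρ)⁴(1 + 4ρ)]. I multiply by 96 - 6 = 90 (four groups and two covariates), then add about 13 for fitting 13 extra parameters.

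| ρ | per subject | × 90 | + 13 | simulated disagreement |
|---|---|---|---|---|
| 0.3 | 0.261 | 23.5 | 36.5 | about 78% |
| 0.5 | 0.523 | 47.1 | 60.1 | about 45% |
| 0.7 | 0.788 | 70.9 | 83.9 | about 4% |

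The pattern fits the thresholds. At 0.3 the gain sits between them, at 0.5 it sits on the BIC threshold, and at 0.7 it clears both.

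**3. Which correlation is plausible?**
- *Change scores.* With equal, independent test-retest error at Screening and follow-up, covariance is σ² and variance 2σ², so ρ = 0.5.
- *Raw scores.* Assume baseline uniform on 16-84% with binomial scoring of 50 words. Within each half of the 50% split the between-subject variance is 0.34²/12 = 0.0096. The mean binomial variance is (0.25 - 0.68²/12)/50 = 0.0042. So ρ ≈ 0.0096/0.0138 ≈ 0.70.

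**4. Overall contrast if AR(1) is fitted to constant correlation.** The ratio of model to true standard error is the square root of [5 + 2(4ρ + 3ρ² + 2ρ³ + ρ⁴)]/(5 + 20ρ). The type I error is 2[1 - Φ(1.96 × ratio)].

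| ρ | ratio | type I error |
|---|---|---|
| 0.3 | 0.856 | 9.3% |
| 0.5 | 0.861 | 9.1% |
| 0.7 | 0.900 | 7.8% |
| 0.85 | 0.945 | 6.4% |

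With three visits the ratio is 0.955-0.984 and the error 5.4-6.1%.

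**5. After selection (simulation, complete data, five visits).**
- AICc decides: 4.7-5.0% at ρ = 0.3, 0.5 and 0.7.
- BIC decides: 9.8%, 6.1% and 4.8%.
- AR(1) exactly true: 4.8% under either structure.

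**6. Scale used for selection.** At baselines of 16% and 84%, the binomial SD of absolute change is 100 × √(2 × 0.16 × 0.84/50) = 7.3 points. On the relative scale this is 7.33/16 = 45.8% against 7.33/84 = 8.7%, a five-fold spread.

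**7. Carry-over.** In simulated trials with binomial noise only, BIC chose UN in 63% of trials on relative change, 45% on absolute change and 97% on the raw score. One selector does not speak for all.

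**The case against.** The strongest reply is that error rates with AR(1) always fitted are not those of the SAP's procedure, which fits both structures and keeps the better one. That stands. In eight scenarios, including rising variance, selection by AICc kept the error at 4.2-5.8%. Material inflation needs BIC to decide, together with weak persistent correlation or, for the Day 210 contrast, decaying correlation with rising variance (about 10%).

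Three stronger readings are tempting, and the documents do not support them.
- *That AR(1) makes the overall contrast too precise in general.* It does so only if correlation persists, and the documents give no correlations. Even with AR(1) fitted throughout, the Day 210 contrast was at 4.9% in three of four simulated patterns. It reached 9.8% only under random-walk drift.
- *That the choice rests on the noisiest endpoint.* The SAP does not rank endpoints by noise. Relative change drives selection only for WR and WIN; for audiometry, "For the audiometry analyses, the covariance structure will be identified by comparing model fit for the mean overall Pure Tone Average (PTA", and for tinnitus, "the TFI total score will be used to identify the covariance structure for all TFI endpoint analyses". Relative change is the most heteroscedastic of the WR change scales checked, but for a 10-point gain its standardised effect is 1.01 against 1.09 (absolute) and 1.13 (arcsine). UN across visits does not cure variance that depends on baseline.
- *That a different structure at interim and final is itself an error.* SAP 7.1.5 discloses it, and the models span three and five visits.

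Materiality is also limited: p-values are descriptive and no decision rule uses them.

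**Conclusion.** The concern holds in a conditional form. The missing tie-break is a fact of the text, and the 27-versus-59 gap is arithmetic under the usual REML definitions. How often it bites depends on the unknown correlation: about 78%, 45% and 4% of trials at 0.3, 0.5 and 0.7. The simple error model points to about 0.5 for change scores, so the 0.3 figures are the unfavourable end.

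If AR(1) is adopted while correlation persists, the overall-contrast standard error is about 6-14% too small at five visits, and the interim error is at most about 6%. The harm arises mainly when BIC decides: about 10%, 6% and 5% after selection. It is absent if AR(1) is true, and was not seen when AICc decides.

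These figures assume complete data and 24 subjects per group. The effect is on the accuracy of reported standard errors, intervals and p-values. The SAP should be changed, but the trial does not turn on it.

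**What to change.** - Prespecify UN with Kenward-Roger degrees of freedom for every MMRM with more than one post-baseline visit, at interim and final.
- Give an ordered fallback for non-convergence: heterogeneous Toeplitz, then heterogeneous compound symmetry, each with sandwich standard errors.
- Delete the AR(1) candidate and the AICc/BIC step from SAP 7.1.5, 7.3.4, 7.4.4, 7.5.5, 7.7.1 and 7.8.1. The sentence allowing different structures at interim and final then goes too.
- In 7.9, drop the structure choice for HSI change, which has a single post-baseline visit (Day 210).

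A smaller repair is to name AICc as the deciding criterion, or to default to UN on disagreement. That closes the gap but keeps the carry-over between endpoints.

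**Cost.** SAP wording and less programming. UN estimates 15 covariance parameters from 96 subjects. When AR(1) was true, simulation on complete data showed no precision cost (standard error ratio 0.997). Convergence could become a problem if much data are missing, which is why the fallback order should be written down.

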#### 7.3.5. Improvement $\geq 10\%$ (5 words) in percentage of recognized words

- *Computation of the Endpoint*

Improvement  $\geq 10\%$  in percentage of recognized words at each post-baseline visit for treated ears will be computed as 1 if the absolute percent change from baseline in percentage of recognized words  $\geq 10\%$  and as 0, otherwise where absolute percent change from baseline is non-missing.

- *Analysis of the Endpoint*

The incidence of improvement  $\geq 10\%$  in percentage of recognized words at each post-baseline visit for treated ears will be summarized using frequencies and percentages by visit and treatment group for subjects in the FAS.

In treated ears only for subjects in the FAS, treatment group comparisons for incidence of improvement  $\geq 10\%$  in percentage of recognized words may be analyzed using a generalized estimating equation based on the binomial distribution with logit link. The fixed covariates may include treatment group, WR score at baseline ( $< 50\%$  versus  $\geq 50\%$ ), etiology of hearing loss (SSNHL versus NIHL), visit, and interaction between visit and treatment group. Covariates for WR score at baseline and etiology of hearing loss may be dropped if the model fails to converge. A random effect for within-subject, repeated measures variability may be included. The treatment group differences analyzed will be between each FX-322 group (including the pooled FX-322 group) versus placebo, and comparisons between the individual FX-322 groups (excluding the pooled FX-322 group). Odds ratios, 95% CIs, and p-values may be reported and comparisons will be made by visit and overall.

- *Sensitivity Analyses of the Endpoint*

The analyses will be repeated for subjects in the PPAS.

#### 7.3.6. Arcsine-transformed WR

- *Computation of the Endpoint*

The arcsine-transformed WR (Studebaker, 1985) will be computed by visit for treated ears as

$$RR = \frac{w}{w + 1} + \frac{w}{w + 1}$$

where “R” is the transformed radians, “w” is the frequency of words recognized, and “n” is the number of words in the word test (n = 50 for WR assessments).

- *Analysis of the Endpoint*

The arcsine-transformed WR will be summarized descriptively for treated ears using the approach described in Section 7.3.1 for subjects in the FAS.

Treatment group comparisons will be performed using the approach described in Section 7.3.4 for subjects in the FAS.

- *Sensitivity Analyses of the Endpoint*

The analyses will be repeated for subjects in the PPAS.

### 7.3.7. WR Categories

- *Computation of the Endpoint*

Using the percentage of recognized words in Section 7.3.2 by visit and for each ear, percentages will be categorized as follows, using the Schoepflin (2012) justification:

- Excellent: >85%
- Good: 68 to 85%
- Fair: 51 to 67%
- Poor: 33 to 50%
- Very Poor: 15 to 32%
- Extremely Poor: <15%

- *Analysis of the Endpoint*

The distribution of WR categories at each baseline and post-baseline visit for treated ears will be summarized using frequencies and percentages by visit and treatment group for subjects in the FAS.

Bar charts will be created for the distribution of WR categories at each baseline and post-baseline visit for treated ears by visit and treatment group for subjects in the FAS.

- *Sensitivity Analyses of the Endpoint*

With the exception of the bar charts, the analyses will be repeated for subjects in the PPAS.

### 7.3.8. Shift in WR Categories

- *Computation of the Endpoint*

Using the WR Categories in Section 7.3.7 by visit for treated ears, shifts from baseline to each post baseline-visit will be computed (e.g., Fair to Good).

- *Analysis of the Endpoint*

The distribution in the shift in WR categories from baseline to each post-baseline visit for treated ears will be summarized using frequencies and percentages by visit and treatment group for subjects in the FAS.

- *Sensitivity Analyses of the Endpoint*

The analyses will be repeated for subjects in the PPAS.

### 7.3.9. Clinical Improvement in WR, using Thornton-Raffin Confidence Intervals ( $CI_{TR}$ )

- *Computation of the Endpoint*

Clinical improvement in WR at post-baseline visits for treated ears will be defined by comparing Thornton-Raffin (1978) 95% confidence intervals ( $CI_{TR}$ ) (Section 14.1) at the baseline visit versus the percentage of recognized words at the post-baseline visits. It will be defined as 'Improved' if the subject's post-baseline score is higher than the upper limit of the subject's baseline 95%  $CI_{TR}$ , as 'No change' if the post-baseline score falls within or on the bounds of the baseline 95%  $CI_{TR}$ , and 'Reduction' if the post-baseline score is lower than the baseline lower limit of the 95%  $CI_{TR}$ .

The Thornton-Raffin 95%  $CI_{TR}$  reported in Section 14.1 will be used directly and not computed.

- *Analysis of the Endpoint*

The incidence of clinical improvement in WR (Improvement, No Change, Reduction) based on  $CI_{TR}$  at each post-baseline visit for treated ears will be summarized using frequencies and percentages by visit and treatment group for subjects in the FAS.

Scatter plots will be used to summarize clinical improvement in the percentage of recognized words (Section 7.3.2) in treated ears. The percentage of recognized words at baseline will be plotted on the x-axis and the percentage of recognized words post-baseline will be plotted in the y-axis, with a separate plot for each post-baseline visit. The baseline Thornton-Raffin 95% confidence intervals in Section 14.1 will be overlaid in the plot.

In treated ears only for subjects in the FAS, treatment group comparisons for incidence of clinical improvement in WR may be analyzed using a generalized estimating equation based on the multinomial distribution with generalized logit (nominal) link. The fixed covariates may include treatment group, WR score at baseline (<50% versus  $\geq$ 50%), etiology of hearing loss (SSNHL versus NIHL), visit, and interaction between visit and treatment group. Covariates for WR score at baseline and etiology of hearing loss may be dropped if the model fails to converge. A random effect for within-subject, repeated measures variability may be included. The treatment group differences analyzed will be between each FX-322 group (including the pooled FX-322 group) versus placebo, and comparisons between the individual FX-322 groups (excluding the pooled FX-322 group). Proportional odds ratios, 95% CIs, and p-values may be reported and comparisons will be made by visit and overall.

- *Sensitivity Analyses of the Endpoint*

With the exception of the scatter plots, the analyses will be repeated for subjects in the PPAS.

#### 7.3.10. Clinical Improvement in WR, using Carney Schlauch Confidence Intervals (CICS)

- *Computation of the Endpoint*

Clinical improvement in WR at post-baseline visits for treated ears will be defined by comparing Carney Schlauch (2007) 95% confidence intervals (CICS) (Section 14.2) at the baseline visit versus the percentage of recognized words at the post-baseline visits. It will be defined as 'Improved' if the subject's post-baseline score is higher than the upper limit of the subject's baseline 95% CICS, as 'No change' if the post-baseline score falls within or on the bounds of the baseline 95% CICS, and 'Reduction' if the post-baseline score is lower than the baseline lower limit of the 95% CICS.

The Carney Schlauch 95% CICS reported in Section 14.2 will be used directly and not computed.

- *Analysis of the Endpoint*

Descriptive summaries, scatter plots, and treatment group comparisons may be performed for clinical improvement in WR (Improvement, No Change, Reduction) based on CICS as described in Section 7.3.9. The Carney Schlauch 95% confidence intervals will be utilized instead of the Thornton-Raffin 95% confidence intervals.

- *Sensitivity Analyses of the Endpoint*

With the exception of the scatter plots, the analyses will be repeated for subjects in the PPAS.

